- b. Outline the protocol, corresponding it to the specific aims; identify the data or endpoints to be analyzed to reach the specific aims. All eligible patients will be seen in the pre-operative holding area to discuss the study. Informed consent will be obtained at that time. The patient will be randomized to one of three groups by random envelope selection. Group 1 will receive a TAP block with a total of 60 mL 0.25% bupivacaine hydrochloride. Group 2 will receive a TAP block with a total of 20 mL of liposomal bupivacaine and 40 mL normal saline. Group 3 will receive a TAP block with a total of 20 mL of liposomal bupivacaine and 40 mL 0.25% bupivacaine hydrochloride. Our standard sedation protocol for all patients receiving any nerve block is to provide a maximum of 2 mg midazolam and 100 mcg fentanyl during procedure. The patient will be monitored per our routine practice standards. The patients will undergo the surgical procedure with general anesthesia as directed by the attending anesthesiologist. All patients will receive 30 mg ketorolac IV. If ketorolac is contraindication, the patient will receive 1000 mg acetaminophen IV. The patient will be recovered and receive routine post-operative care. Patients will be assessed immediately post-operatively in the post-anesthesia care unit (PACU), and one time during each of the following time periods: 0-24 hrs post-operatively, 25-48 hours post-operatively, and 49-72 hours post-operatively. Primary outcomes are total opioid consumption, time to the first opioid administration, and pain score during the above mentioned time periods. Secondary outcomes are patient satisfaction, length of stay in hospital, timing of ambulation, presence of nausea and vomiting, evidence of local anesthetic toxicity and any postoperative hemodynamic instability.
- c. Discuss potential limitations and difficulties in the protocol. We don't anticipate any difficulties with this protocol since patients typically receive a TAP block for post-operative analgesia for open abdominal hysterectomy at Henry Ford Hospital. One limitation of our protocol is that it is not double-blinded. Liposomal bupivacaine is white and distinctive from bupivacaine hydrochloride. Therefore, the anesthesiologist performing the block cannot be blinded to group selection. All other care team members including anesthesia team, surgical team, and floor nurses, will be blinded to the group selection.

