- d. Provide a tentative schedule for conducting and completing this project and, if applicable, the multicenter study. We anticipate one year to recruit patients and collect data. Data analysis will take a few months after study completion.
- e. **Data collection:** Submit a copy of the data collection tool or list the data fields to be collected (review IRB policy, Access to Medical Records for Research). Age, ASA classification, height, weight, BMI, indication for hysterectomy, surgeon, duration of surgery, time of TAP block, time to first break-through analgesic, cumulative analgesic doses and pain scores at rest and with movement in PACU and in the following time periods: 0-24 hours, 25-48 hours, 49-72 hours. in 6 hr increments for the first 24hrs, then every 12 hrs for the next 24 hours. Satisfaction (ie not satisfied, satisfied, very satisfied), length of stay in the hospital, presence of ambulation, presence of nausea and vomiting, evidence of local anesthetic toxicity, presence of hypotension.

7. DATA ANALYSIS: Describe the analysis of the data and relate this to the specific aims in detail. Case reports and medical record reviews also require a description of the planned data analysis (ie. descriptive, observational). The Committee recommends free consultation with the Division of Biostatistics and Research Epidemiology before IRB submission. Many clinical measurements will be recorded post operation. Some are one-time measurements such as total opioid consumption, and some are repeated measurements such as pain scores. Total 8-9 measuring times for those

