repeated outcomes. Ideally these time points are at baseline, 6 hours, 12 hours, 18 hours, 24 hours, 36 hours, 48 hours, 60 hours and 72 hours. Continuous variables will be summarized with n, mean, standard deviation and range. Frequency counts and percentage will be provided for categorical data. Estimates for averages and proportions will also include 95 % confidence intervals. One-way Analysis of Variance(ANOVA) will be used to assess the efficacy of three anesthetic bupivacaine formulas (G1: bupivacaine HCL; G2: liposomal bupivacaine ; G3: liposomal bupivacaine + bupivacaine HCL) on total opioid consumption, patient satisfaction, length of stay in hospital as well as timing of ambulation. Generalized Estimating Equations (GEE) will be utilized to evaluate the effects of these three anesthetic formulas on repeated measures of pain scores, presence of nausea and vomiting, evidence of local anesthetic toxicity and any postoperative hemodynamic instability. Cox proportion hazard models will be applied to assess the effect of these anesthetic formulas on the time to first opioid administration. The statistical analysis will be obtained by using SAS 9.4 and the tests are claimed to be significant if the p- values are less than 0.05.

8. JUSTIFICATION FOR NUMBER OF SUBJECTS OR DATA:

- a. State the number of subjects or data points to be analyzed in the project at this institution and the total number for multicenter studies. The Committee recommends consultation with the Division of Biostatistics and Research Epidemiology [contact]. Total 90 subjects are expected given at least 80% recruitment rate of total 100-150 patients undergo open abdominal hysterectomy at Henry Ford Hospital each year.
- b. Describe the statistical justification for this number of subjects or data points. Total 90 patients (30 for each of these 3 groups) will have 80% power to detect the effect size of 0.33 by using One- Way ANOVA for assessing the effects of three formulas on total opioid consumption; and an effect size of 0.24 can be detected with 80% power assuming 0.5 correlation among repeated measures by using repeated One - Way ANOVA for assessing the effects of three formulas on pain scores.

FORM A

HENRY FORD HEALTH SYSTEM (IRB) DRUG/SUBSTANCE INFORMATION

(This form must be completed for each individual drug or substance -investigational or marketed- that is being administered as part of this research study)

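### Section 7 lists an undefined baseline pain score (most likely the PACU score), and no pain score is taken before the block to serve as a covariate

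*Combined protocol and SAP*

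**What the plan says.** - **Section 7 (data analysis)** introduces the outcomes with "Many clinical measurements will be recorded post operation" and gives the number of repeated assessments as "Total 8-9 measuring times for those" outcomes. It then lists them: "Ideally these time points are at baseline, 6 hours, 12 hours", followed by 18, 24, 36, 48, 60 and 72 h. Baseline is not defined and PACU does not appear. Pain scores go into a GEE comparing the three formulations. No covariate and no change-from-baseline outcome is stated.
- **Section 6b** sets the order of events: holding area, consent, randomization, block, surgery, recovery. The first assessment is in PACU: "Patients will be assessed immediately post-operatively in the post-anesthesia care unit (PACU"). Pain score in PACU and in the three later periods is one of the primary outcomes.
- **Section 6e** lists the fields: "pain scores at rest and with movement in PACU and in the following time periods: 0-24 hours, 25-48 hours, 49-72 hours", with the grid "in 6 hr increments for the first 24hrs, then every 12 hrs for the next 24 hours". No pain field precedes PACU.
- **Section 8b** gives a detectable effect size of 0.24 for pain at 80% power, with 30 patients per group and correlation 0.5 among repeated measures.

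**The concern.** In a trial, baseline ordinarily means a value taken before treatment, and analysts often adjust for it or subtract it. Here the word heads a list of outcome times, while the earliest scheduled score comes after the block. A reader therefore cannot tell from section 7 alone which score is meant or what part it plays in the model.

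Two things are at stake. First, the PACU score is the earliest test of the hypothesis in section 3a that the mixture is better straight after surgery as well as later, so it should be clearly marked as an outcome. Second, on any reading of the label, the trial has no pre-treatment pain value with which to sharpen the comparison on a primary outcome or to describe the arms at entry.

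**Working it through.** **Step 1: what baseline most plausibly means.**
- Section 7 describes its measurements as taken after the operation.
- The grid in 6e gives PACU (1), then 6, 12, 18 and 24 h (4), then 36 and 48 h (2), which makes 7. One or two scores in the 49-72 h window bring this to 8 or 9, matching section 7's total if baseline is the PACU score. (6e states no frequency after 48 h; section 7's list has 60 and 72 h. The count uses 6e's grid, not 6b's single assessment per period.)
- 6b makes PACU part of the primary pain outcome. If baseline were pre-operative, PACU would be missing from section 7's list.
- The same list serves all repeated outcomes, including local anesthetic toxicity and postoperative hemodynamic instability, for which a pre-block value has little meaning.

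All four points favour PACU as the time-0 outcome.

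**Step 2: reproduce the plan's figure.** Inputs from 8b and section 7: N = 90, three groups, f = 0.24, ρ = 0.5, m = 8 or 9, α = 0.05. The variance of a patient's mean score, relative to a single score, is v = [1 + (m − 1)ρ]/m. The noncentrality is λ = N f²/v, on 2 and 87 df.
- m = 8: v = 4.5/8 = 0.5625; λ = 90 × 0.0576/0.5625 = 9.216; power 76.6%.
- m = 9: v = 5/9 = 0.5556; λ = 5.184/0.5556 = 9.331; power 77.1%.

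The large-sample chi-square version gives 78.1% and 78.6%. At m = 9 it reaches 80% at f = 0.244, which rounds to the stated 0.24. The plan's figure is therefore reproduced approximately, as a time-averaged group effect.

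**Step 3: add a pre-block score as a covariate.** Assume it correlates r with every later score. The residual variance is v − r², so λ = 5.184/(0.5556 − r²), on 2 and 86 df. The plan gives no r.

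| r (assumed) | v − r² | λ | Power, m = 9 |
|---|---|---|---|
| 0 | 0.5556 | 9.33 | 77.1% |
| 0.1 | 0.5456 | 9.50 | 77.9% |
| 0.2 | 0.5156 | 10.06 | 80.3% |
| 0.3 | 0.4656 | 11.14 | 84.4% |

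At r = 0 the lost degree of freedom costs nothing visible.

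**The case against.** **Stronger readings that a reader might infer.**
- *The pain analysis is diluted.* If a pre-block score, which cannot carry a treatment effect, were averaged in as one of nine outcome times, the effect would shrink by 8/9: λ = 90 × (0.24 × 8/9)²/0.5556 = 7.37, and power would fall from 77.1% to 66.4%. But this needs a score that the plan never collects, so the loss cannot arise from the scheduled data.
- *The early difference is adjusted away.* If the PACU score were a covariate for the eight later scores and the effect were constant, the effect would halve: λ = 90 × 0.12²/(0.5625 − 0.25) = 4.15, and power would be about 42%. But section 7 applies the GEE to the repeated scores themselves and states neither a covariate nor a change score.

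Neither figure describes the planned analysis.

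**The case against making the point at all.** The arms are randomized, so comparing post-operative scores is valid without a pre-block value, and leaving out an optional covariate is not an error. The gain rests on correlations found nowhere in the documents. At 0.1 it is under one percentage point. Section 5a excludes patients with a chronic pain condition, so pre-block scores may vary little.

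All of this stands, and it limits the point to an inexpensive improvement plus a wording correction. It does not remove the point: the label is undefined, the PACU reading has to be worked out by counting across sections, and the contact at which the extra score could be taken already exists.

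**Conclusion.** The point holds as a clarification and an inexpensive gain in precision. Read as the PACU score at time 0, baseline is a legitimate post-treatment outcome and the pain GEE is neither diluted nor biased. The trial does, however, collect no pre-treatment pain value for a primary outcome. Adding one as a covariate would raise power from about 77% to 78%, 80% or 84% at assumed correlations of 0.1, 0.2 or 0.3, with no visible loss at zero.

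These figures assume equal correlation of 0.5 among nine post-treatment scores, f = 0.24, all 90 patients analysed, a constant effect over time and a test of the time-averaged group difference. Section 7 does not specify that last feature. With the chronic-pain exclusion, the true gain may lie at the low end.

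**What to change.** - **Sections 6b and 6e:** add one pain score, at rest and with movement, in the holding area after consent and before sedation and block.
- **Section 7, model:** enter that score only as a covariate in the pain GEE, not as one of the repeated outcomes.
- **Section 7, label:** rename the first outcome time PACU. State that it is an outcome, and that it is never used as an adjustment variable or to form change scores.

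The cost is one short assessment at a contact that already takes place, its entry on the data form, and small wording changes in three sections. The downside is one extra item for patients just before surgery. If the sponsor prefers not to add it, the change of label should still be made before the data are analysed.

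### Baseline fields are collected but no primary analysis is planned to use them; a short pre-specified adjustment is a cheap, though not free, gain in precision

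*Combined protocol and SAP*

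**What the plan says.** Section 6b names three primary outcomes: total opioid consumption, time to first opioid and pain score. It allocates patients by envelope and states no stratification factor.

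Section 6e lists the fields to be recorded, beginning "Age, ASA classification, height, weight, BMI, indication for hysterectomy, surgeon". It does not say when each is recorded, but age, ASA class and BMI are by nature known before the block, and so is the preoperative indication.

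Section 7 gives one method per outcome:

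- **Total opioid consumption** (with satisfaction, length of stay and timing of ambulation): "One-way Analysis of Variance(ANOVA) will be used to assess the efficacy of three anesthetic bupivacaine formulas". Covariates are excluded by the choice of method.
- **Pain scores:** GEE, described only by the effect of the three formulations. Covariates are neither named nor ruled out.
- **Time to first opioid:** Cox models, described in the same way and equally silent on covariates.

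Beyond general descriptive summaries, section 7 gives the baseline fields no role.

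Section 8b sizes the trial on the unadjusted test: "Total 90 patients (30 for each of these 3 groups) will have 80% power to detect the effect size of 0.33".

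**The concern.** If baseline fields predict opioid use or pain, leaving them out keeps their share of the variance in the error term, so the treatment comparison is less precise than the collected data allow. The design has little slack, because the sample size just reaches its power target.

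With 30 per arm, chance imbalance on a given covariate will sometimes be noticeable, and neither stratification nor the model deals with it. For a standardised continuous covariate, the SD of the difference between two arm means is √(2/30) = 0.26. The chance that some pair of the three arms differs by more than 0.5 SD is about 13%.

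The silence on the GEE and Cox models matters separately. If covariates are not settled in advance, they can be chosen after the results are seen, and there are three primary outcomes, each tested at 0.05.

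**Working it through.** **Inputs from the documents.** N = 90, 30 per group; effect size 0.33, read as Cohen's f for the three-group F test; stated power 80% (section 8b). Alpha 0.05 (section 7).

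**Assumed inputs.** The documents give no SD, R² or covariate–outcome correlation. R² is therefore taken over a range from 0 to 0.20. Covariate degrees of freedom are q = 4: age 1, BMI 1, ASA class 1, indication as two levels 1. No dropout is allowed for, since none is stated.

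**Step 1: the plan's own figure.** The noncentrality is λ = N·f² = 90 × 0.33² = 9.801, on 2 and 87 df. Power is 79.3%. The f that gives exactly 80% is 0.333, which rounds to 0.33, so the stated figure reproduces. It rests on the unadjusted test.

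**Step 2: ANCOVA, charging only the lost degrees of freedom.** λ = 9.801/(1 − R²), on 2 and 87 − 4 = 83 df.

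**Step 3: ANCOVA, also charging for chance imbalance.** When covariates differ between arms by chance, the adjusted contrast loses some precision. This is approximated by multiplying λ by (86 − q)/86 = 82/86 = 0.953, on the same df.

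| R² (assumed) | λ, step 2 | Power, step 2 | λ, step 3 | Power, step 3 | Step 3 minus 79.3% |
|---|---|---|---|---|---|
| 0 | 9.80 | 79.2% | 9.35 | 77.1% | −2.2 |
| 0.05 | 10.32 | 81.3% | 9.84 | 79.3% | 0.0 |
| 0.10 | 10.89 | 83.5% | 10.38 | 81.6% | +2.3 |
| 0.20 | 12.25 | 87.8% | 11.68 | 86.1% | +6.8 |

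**Step 4: break-even.** Setting step 3 power equal to 79.3% gives R² = 0.048 for q = 4. A longer list raises the bar: R² = 0.072 for q = 6 and 0.096 for q = 8.

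The degrees of freedom alone cost about 0.1 point. Most of the cost of useless covariates is the imbalance term, so the list should be short.

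No corresponding size is claimed for the pain or Cox analyses. The arithmetic above concerns total opioid consumption only.

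**The case against.** The strongest reply is that nothing here is an error. One-way ANOVA in a randomised 1:1:1 trial is valid, and section 8b is based on that same test. Chance imbalance does not bias the estimator over repeated randomisation, and its contribution is already in the standard error. That stands: the point is about efficiency and pre-specification, not validity.

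Three stronger readings are tempting, and the documents do not support them:

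- **Adjustment is free power.** No document shows that these fields predict the outcomes. Section 6e lists no baseline pain score and no preoperative opioid use, and section 5a excludes patients with a chronic pain condition. If R² is near zero, adjustment costs about 2 points. Charging only degrees of freedom would hide that cost and overstate the gains by roughly 2 points.
- **Every analysis is unadjusted.** This is explicit only for the ANOVA outcomes. For the GEE and Cox models, section 7 is silent.
- **Adjustment leaves the question unchanged.** That is so for the linear model on mean opioid consumption. It is not so for Cox, where the hazard ratio is non-collapsible and adjustment moves the target from a marginal to a conditional hazard ratio.

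A further caution also stands. Section 6e says only that indication is recorded. If it were coded from surgical pathology, it would be known after randomisation and would not be a baseline covariate.

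**Conclusion.** The point holds as a recommended improvement. Total opioid consumption is to be analysed with treatment alone, the other two primary models name no covariates, and usable baseline fields are collected without an analytic role.

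For total opioid consumption at f = 0.33, pre-specified adjustment with 4 df yields roughly nothing at R² = 0.05, 2 points at 0.10 and 7 points at 0.20, against a loss of about 2 points if the covariates are not prognostic. It also corrects the estimate for whatever imbalance arises in those covariates.

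These figures rest on an assumed R², on reading 0.33 as Cohen's f, on complete data, and on the approximation used for chance imbalance. The absence of any planned covariate is clear from the text; the size of the gain cannot be settled from it.

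**What to change.** In section 7:

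1. Replace the one-way ANOVA for total opioid consumption with ANCOVA on treatment plus age, BMI, ASA class and preoperative indication as a two-level factor. Fix the list and coding before any outcome data are examined, at about 4 df in all. Define indication by the preoperative diagnosis.
2. Keep the unadjusted one-way ANOVA as a sensitivity analysis; it remains the test that section 8b is sized on.
3. Use the same list in the GEE for pain scores. If it is also used in the Cox model, state that the hazard ratio is conditional on those covariates. If any primary model is to stay unadjusted, say so.
4. Do not adjust for duration of surgery or PACU scores, which arise after the block.

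The cost is a sentence or two of text and about 4 degrees of freedom. No new data collection is needed, and the sample size does not change. The risk is the loss of about 2 points of power if the covariates turn out to be uninformative.

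### GEE is the only between-group method named for local anesthetic toxicity, and if the per-patient risk is below about 5% at least one 30-patient arm will more likely than not have no events, leaving its contrasts without a finite estimate

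*Combined protocol and SAP*

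**What the plan says.** Item 6b lists toxicity among the secondary outcomes: "Secondary outcomes are patient satisfaction, length of stay in hospital, timing of ambulation, presence of nausea and vomiting, evidence of local anesthetic toxicity", followed by hemodynamic instability. The data fields in item 6e include "evidence of local anesthetic toxicity, presence of hypotension". Neither place defines toxicity or gives an expected rate.

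Section 7 states that "Generalized Estimating Equations (GEE) will be utilized to evaluate the effects of these three anesthetic formulas on repeated measures of pain scores". The same sentence goes on to nausea and vomiting and then to "evidence of local anesthetic toxicity and any postoperative hemodynamic instability". No other between-group method is named for toxicity. The link function, the working correlation, the type of test (Wald or score) and any fallback for sparse data are not stated. The significance rule is that "the tests are claimed to be significant if the p- values are less than 0.05".

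Section 7 also plans counts and percentages for categorical variables, with 95% confidence intervals for proportions. The interval method is not named.

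Item 8b gives the arm size: "Total 90 patients (30 for each of these 3 groups) will have 80% power to detect the effect size of 0.33". That calculation concerns total opioid consumption. No power or precision is given for toxicity.

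**The concern.** A GEE for a binary outcome normally models the log-odds of an event. In an arm where no patient has an event, the estimated log-odds run to minus infinity, and so does any log-odds ratio involving that arm. Software does not always stop when this happens. It may print a very large coefficient with a standard error that is missing, huge or far too small.

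With 30 patients per arm, an uncommon event can easily be absent from an arm. The plan would then rest its toxicity comparison on an unreliable p-value read against a 0.05 rule. A single event in the combination arm could be reported as strong evidence of harm, and a single event in the control arm as strong evidence of protection.

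**Working it through.** **The plan's own figure.** For the one-way ANOVA in item 8b (N = 90, three groups, f = 0.33, alpha 0.05), the noncentrality is 90 × 0.33² = 9.80 on 2 and 87 degrees of freedom. The power is 0.793, in line with the stated 80%. This confirms the reading of 30 per arm. It says nothing about toxicity.

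**Inputs for toxicity.** The 30 patients in each of three arms come from item 8b. The per-patient risk p is an assumption, because the documents give none. It is varied, taken as equal in all arms, and applied with all 30 patients per arm assessed.

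**Chance of empty arms.** Let q = (1 − p)^30 be the chance that one arm has no event. Then:

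- at least one arm empty: 1 − (1 − q)³
- two or more arms empty: 3q²(1 − q) + q³
- all three empty: q³

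| Assumed risk p | q | At least one empty | Two or more empty | All three empty |
|---|---|---|---|---|
| 1% | 0.740 | 98% | 83% | 40% |
| 2% | 0.545 | 91% | 57% | 16% |
| 5% | 0.215 | 52% | 12% | 1.0% |
| 10% | 0.042 | 12% | 0.5% | <0.1% |

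The first probability passes 50% at a risk of about 5.1%. Repeated assessment ("Total 8-9 measuring times for those" repeated outcomes, according to section 7) does not help, since an arm with no affected patient has no event at any visit.

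**What the model does with an empty arm.** Binomial-logit GEE was fitted in Python (statsmodels) to constructed data with 4 and 9 visits, under independence and exchangeable working correlations. Each affected patient had one event. Events are listed in the order Group 1 / Group 2 / Group 3.

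- **0/0/1:** log-odds ratio for Group 3 against Group 1 about +23, robust standard error 0.99, p < 0.0001.
- **1/0/0:** log-odds ratios about −23, standard errors about 1.0, p < 0.0001.
- **0/1/2:** coefficients of about 22 against the empty arm. Standard errors were undefined under independence; under the exchangeable structure they were partly undefined or ranged from 11 to 206.
- **0/2/3:** contrasts against the empty arm diverge, but Group 2 against Group 3 is ordinary (4 visits: log-odds ratio −0.41, standard error 0.89).
- **1/1/2:** ordinary fit, with standard errors of 1.2 to 1.4 for the group contrasts.

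The software reported convergence for the patterns 0/0/0, 1/0/0, 0/1/2 and 1/1/2, so a convergence flag would not reveal the problem. SAS output may differ in detail, but the estimate for an empty arm has no finite value in any package.

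**What exact methods give.** The Clopper-Pearson two-sided 95% upper limit for 0/n is 1 − 0.025^(1/n): 11.6% for 0/30 and 4.0% for 0/90. A simple Wald interval at 0/30 has standard error √(0 × 1/30) = 0 and collapses to 0% to 0%.

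For the Fisher-Freeman-Halton test with all k events in one arm, p = 3 × C(30,k)/C(90,k) for k of 2 or more. This gives 0.33 for two events, 0.10 for three and 0.032 for four. A single event gives p = 1.

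**The case against.** The strongest reply is that the loss is limited. Section 7 already plans counts, percentages and 95% confidence intervals, which describe toxicity without any model. A reader might infer that the plan yields no usable safety estimate at all. The documents do not support that: what is at risk is the between-group comparison. Even so, the interval method is unnamed, and a Wald interval would be useless at 0/30.

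A reader might also infer that the whole comparison fails once one arm is empty. It does not. One empty arm removes only the contrasts against it. All pairwise contrasts are lost only when two or more arms are empty, which is the less likely event in the table. A score test of the overall group effect also avoids estimating each arm: with events 0/2/3 it gave chi-square 5.00, p = 0.08. The plan does not say that a score test will be used, however, and it names no link. Logit is the usual choice and is assumed here.

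Toxicity cannot be called rare on the documents' authority. They give neither a rate nor a definition, and if mild symptoms count as "evidence of local anesthetic toxicity" the risk might be near 10%, where the problem mostly recedes. That stands, and it makes the point conditional. Nor is toxicity the protocol's main safety outcome: it is one of several secondary outcomes, and neither specific aim concerns safety.

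Finally, the exact test has little power with few events. That also stands. It does not excuse a method that can print strong significance from one event.

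**Conclusion.** The point holds in conditional form. GEE is the only between-group analysis named for toxicity, and with 30 per arm it is unsuitable if events are uncommon. Below a per-patient risk of about 5%, at least one empty arm is more likely than not. At 1% to 2%, the loss of every pairwise contrast is itself more likely than not (83% and 57%). The more serious consequence is a falsely small p-value, because it would pass unnoticed under the 0.05 rule.

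This rests on three assumptions: a risk that the documents do not give, taken as equal across arms; a logit link; and Wald-type output. The effect is confined to one secondary outcome, and to any other binary secondary outcome that turns out to have an empty arm. The primary outcomes and the sample size are untouched.

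**What to change.** In section 7:

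1. Remove toxicity from the GEE list. Analyse it per patient, as any event up to 72 hours, and report the number and percentage in each arm.
2. State that the 95% intervals already planned will be exact (Clopper-Pearson) for this outcome.
3. Use a Fisher-Freeman-Halton exact test for any group comparison of toxicity.
4. State in advance that the same approach applies to any other binary secondary outcome with an empty arm.

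This takes a few lines of text and needs no extra patients or data. There are two downsides. If events turn out to be common, the time-point model, which could then have been fitted, is given up. And the exact test cannot reach p < 0.05 with fewer than four events in total, so safety conclusions should rest mainly on the counts and exact intervals. A non-significant test should not be read as evidence of equal safety.
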